4.2. Handling of missing data and drop-outs

Missing data, missed training sessions or abandonments are noted in the CRF. Data from patients who discontinue the examination is collected and stored. Drop-outs are not replaced by the recruitment of new participants. If consent is withdrawn, the data already collected will be included in the analysis for scientific and safety reasons. These are only anonymised after the analysis (Art. 32 ClinO-MD).

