
Risk / Benefit Assessment	In this examination, the risk can be classified as minimal. The product is applied as recommended by the manufacturer. The muscle soreness protocol is a protocol that has already been described in the scientific literature.
Objective(s)	The aim of this study is to investigate how local, repeated cold applications affect the recovery phase according to a muscle soreness protocol. Recovery is assessed at 24-hour intervals (up to 72 hours according to the muscle soreness protocol).
Endpoint(s)	
Primary endpoints:
 
 • Sore muscles (VAS 0 – 10 cm) • Inflammation levels (blood sinking velocity, C-reactive protein, creatine kinase) • Muscle swelling (in cm using ultrasound) • Maximum Voluntary Isometric Thigh Contraction (in kg) 
Secondary endpoints
 
 • Surface temperature of the skin (in °C) • Thermal Perception
Investigation Design	Randomized, controlled trial
Statistical Considerations	Repeated measure ANOVA, n=45 subjects
Inclusion- / Exclusion Criteria	
Inclusion Criteria
 
 • Young, healthy adults between the ages of 18 and 30 • No surgical interventions on the musculoskeletal system in the trunk area and lower extremities 
Exclusion criteria
 
 • Current pain conditions: Subjects with acute pain conditions. • Current inflammatory conditions: Presence of inflammation or known inflammatory diseases. • Medication intake (excl. anticonception drugs): Subjects taking medication, with the exception of anticonception drugs. • Pregnant subjects: Women who are pregnant or breastfeeding. • Competitive athletes: Test subjects who practice competitive sports. • Children/adolescents: Subjects under 18 years of age or over 30 years of age. • Non-intact skin conditions (e.g. psoriasis): Skin conditions, such as psoriasis or other non-intact skin conditions. • Known circulatory disorders: Presence of known circulatory disorders. • Cold allergy (Raynaud's syndrome): Allergy to cold or the presence of Raynaud's syndrome. • Previous operations on the upper body or legs: Operations in the areas of the body examined. • Disturbed perception in the thigh: Disturbances in the sensation of temperature or touch in the thigh area. • Diagnosed diseases: Presence of diagnosed diseases that could affect participation in the examination. • Smoking: When the subject smokes.

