δ_i	The difference between the i th treatment agent and the control agent ($\mu_i - \mu_c$) for which the test strength is calculated.
σ	The standard deviation of the responses within each group.
Alpha	The probability of rejecting the null hypothesis that the control mean is equal to the treatment mean described in this row.

Summary statements

A parallel 3-group design (with a control group and 2 treatment groups) is used to test whether the mean for each treatment group is different from the mean of the control group ($H_0: \delta = 0$ versus $H_1: \delta \neq 0, \delta = \mu_i - \mu_c$). The hypotheses are evaluated using two two-sided, two-sample methods. Bonferroni-adjusted t-tests with the same variance and an overall (experimental) Type I error rate (α) of 0.05. The common standard deviation for all groups is assumed to be 2.1. The mean value of the control group is assumed to be 4.72. The treatment means 2.21 and 1.87 with at least 80% test strength to be detected in each case. For the test, the (same) group sample size needed for each of the three groups (control and treatments) is 13 (39 subjects in total). The group sample sizes were calculated using PASS 2023, version 23.0.1.

Sample size taking into account the dropout rate

Group	Dropouts Abandonment Rate	Number of cases/group	Number of cases with drop-out rate	Number of abandoned participants
1 - 3	10%	13	15	2
Total	n/a	39	45	6

Taking into account the drop-out rate

Taking into account a dropout rate of 10%, the group sizes in each study arm should be 15 subjects.

Statistical approach to examine the primary endpoints

The statistical analysis is performed using IBM SPSS Statistics (version 27, IBM Corp., Armonk, NY, USA) and the significance level is set to $p < 0.05$.

In order to be able to determine the differences between groups, a repeated ANOVA analysis is carried out with a factor of 1: time (baseline, 24 hours, 48 hours, 72 hours) and a factor of 2:

intervention (group A, group B, group C) for the recovery parameters (inflammation values, muscle swelling, muscle soreness data, maximum voluntary isometric muscle contraction).

The examination is discontinued if the participants are intolerant to the local cold application. Participants in the IC and DC groups are instructed to cancel a cooling session and contact their contact immediately if they experience symptoms such as severe pain/discomfort as a result of the cooling.

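### Section 4.2 says data recorded before withdrawal will be analysed, but the repeated-measures ANOVA named in 4.1, as ordinarily run, drops any subject with an incomplete series

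*Combined protocol and SAP*

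**What the plan says.** Section 4.2 covers missing data in a few sentences.

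- On withdrawn consent: "If consent is withdrawn, the data already collected will be included in the analysis for scientific and safety reasons".
- On people who stop: "Data from patients who discontinue the examination is collected and stored".
- On gaps: "Missing data, missed training sessions or abandonments are noted in the CRF".
- On replacement: "Drop-outs are not replaced by the recruitment of new participants".

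Section 4.1 gives the method for all recovery parameters: "a repeated ANOVA analysis is carried out with a factor of 1: time (baseline, 24 hours, 48 hours, 72 hours", with group (A, B, C) as the second factor. The synopsis agrees: "Repeated measure ANOVA, n=45 subjects". On software: "The statistical analysis is performed using IBM SPSS Statistics (version 27". No SPSS procedure is named. Neither section defines an analysis set, an imputation rule or a model that accepts incomplete series.

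**The concern.** A classical repeated-measures ANOVA needs all four values from each subject. Someone measured at baseline, 24 h and 48 h who then leaves is removed from that endpoint at every time point, including the three that were measured. One missed blood sample has the same effect for that marker. Followed as it is normally run, the plan therefore gives a completers-only result, while 4.2 tells the reader that earlier data are used.

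Two things are at stake. One is a stated commitment with no method behind it. The other is possible bias in the group comparison if those who leave differ between arms. Section 4.1 provides for stopping when the local cold is not tolerated, a reason that cannot arise in the control arm. Randomisation takes place on the baseline day, before the soreness protocol (section 3.3), so randomised people can be lost after data have been recorded.

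**Working it through.** **1. The plan's own figures.** Inputs from the section 4.1 table: control mean 4.72, cooled means 2.21 and 1.87, SD 2.1, two-sided alpha 0.05 per comparison, 13 per group. For a two-sample t-test the noncentrality is δ / (σ√(2/n)).

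- δ = 2.51: 2.51 / (2.1 × √(2/13)) = 3.05 on 24 df, power 0.8323 (table: 0.83233).
- δ = 2.85: 2.85 / (2.1 × √(2/13)) = 3.46 on 24 df, power 0.9129 (table: 0.91287).
- Drop-out: 13 / 0.9 = 14.4, rounded up to 15 per arm, 45 in total. The table's 2 of 15 (13.3%) is 10% after rounding up.

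The figures reproduce.

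**2. What listwise deletion discards.** Each endpoint has 45 × 4 = 180 scheduled values. If each of the 6 drop-outs has k visits recorded, 6k recorded values are lost:

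| Visits recorded (k) | Values discarded | Share of 180 |
|---|---|---|
| 1 | 6 | 3.3% |
| 2 | 12 | 6.7% |
| 3 | 18 | 10% |

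With only the 72 h visit missing, the ANOVA keeps 39 subjects and 39 × 4 = 156 values. A mixed model keeps 45 subjects and 180 − 6 = 174 values. On made-up data of this shape, the repeated-measures ANOVA in statsmodels refused the unbalanced set and its mixed model used all 174 values. This was not tested in SPSS.

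Sporadic gaps add to the loss. If each of three follow-up values is missed independently with probability m (assumed; the documents give no rate), expected completers are 45(1 − m)³: 42.4, 38.6 and 32.8 for m = 2%, 5% and 10%.

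**3. Power.** Six losses spread evenly leave 13 per arm, the number powered for. With 12 or 11 complete per arm, power for 2.51 cm is 0.799 or 0.760.

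**4. Bias in the group difference.** Assumptions: drop-out occurs after 24 h; 24 h soreness is normal with SD 2.1 and means 2.21 (cooled) and 4.72 (control); P(leave) = 1 / (1 + exp(−(a + b·VAS at 24 h))), with b = 0.5 to 1.0 per cm; between-visit correlation ρ = 0.5 to 0.7. The SD and means are the plan's. The rest is assumed.

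An arm's error at 24 h is e = E(VAS | stays) − μ. At 72 h it is ρe. The error in the comparison is e(cooled) − e(control).

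*Same 13.3% leaving each arm (a set per arm):* e = −0.26 (b = 0.5) or −0.39 (b = 1.0) in both arms. The errors cancel, and the difference is off by about zero.

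*One common rule (a set so that 13.3% leave on average over the two arms):*

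| b | Leave: cooled / control | e: cooled / control | Error in difference, 24 h | Error at 72 h, ρ = 0.5 / 0.7 |
|---|---|---|---|---|
| 0.5 | 7.3% / 19.4% | −0.15 / −0.37 | 0.22 | 0.11 / 0.15 |
| 1.0 | 4.7% / 21.9% | −0.16 / −0.61 | 0.45 | 0.22 / 0.32 |

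The last entry is 0.7 × 0.45 = 0.315. At 24 h the planned −2.51 becomes −2.29 to −2.06, so cooling looks less effective than it is, by 9% to 18% of 2.51. Extra loss of the sorest people from the cooled arms alone would push the other way, so the direction is not known in advance.

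In these scenarios an estimate that also uses the observed 24 h value has about zero bias.

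**The case against.** **The sentence may be about data use, not estimation.** It sits beside a rule on anonymisation and gives safety as a reason. Safety data, Day 1 skin temperature and thermal perception can all be reported without a complete series. Deletion works endpoint by endpoint, and someone who withdraws after the 72 h visit is fully analysed. A reader might infer that withdrawals contribute nothing, or that the promise is impossible to keep. The documents do not support that. They name no SPSS procedure and do not mention listwise deletion, and SPSS also offers mixed models. What stands is that the sentence promises inclusion for scientific reasons too, and no named method delivers it for an incomplete primary endpoint.

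**Another test is mentioned.** Section 4.1 says "The hypotheses are evaluated using two two-sided, two-sample methods", and a t-test per visit would use all available values. But that is the sample-size summary. The paragraph on analysing the primary endpoints names only the ANOVA.

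**The bias need not reach the comparison.** Completers' means in one arm can be too low by 0.13 to 0.53 cm under assumed soreness-related loss (the upper end if the sorest 13% leave). It is tempting to read this as error in the treatment effect. It is not: equal loss of the same kind in each arm cancels. This objection stands, and it limits the point to differential drop-out.

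**The alternative is not bias-free.** Its near-zero bias follows from simulating drop-out on observed values only. If drop-out depends on the unobserved 48 h value, an arm's 72 h mean is still off by 0.06 to 0.11 cm, against 0.13 to 0.28 cm for completers. And anyone who fails the 12-repetition minimum in section 3.3 leaves on Day 1, before any follow-up value exists. Both limits stand.

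**Conclusion.** The mismatch between 4.1 and 4.2 is real and should be corrected. On the plan's own 6 losses, 6 to 18 recorded values per endpoint would go unused.

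A reader might also infer that the trial loses its planned power. It does not if losses stay at 2 per arm: 13 per arm remain, with power 0.832 for the 2.51 cm difference.

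Bias in the group comparison is conditional. It is about zero when the same share leaves each arm by the same mechanism. It is about 0.22 to 0.45 cm at 24 h and 0.11 to 0.32 cm at 72 h under one assumed soreness-driven rule common to the cooled and control arms. Differential loss is plausible because cold intolerance is confined to the cooled arms, but the documents give no drop-out rate by arm. The conclusion also rests on the ANOVA being run in its ordinary complete-case form. If a mixed model was intended, the plan needs to say so.

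**What to change.** In section 4.1, replace the repeated-measures ANOVA with a linear mixed model for repeated measures (SPSS MIXED): group, time and group-by-time as fixed effects, unstructured covariance across visits, Satterthwaite degrees of freedom, and all observed values from every randomised participant in the group drawn. Amend the synopsis to match. In section 4.2, state that this is how data collected before withdrawal enter the analysis.

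A stated imputation rule with a defined analysis set would also reconcile the two sections. The mixed model is simpler and stays in the same software.

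The cost is a change of wording and long-format data, with no extra participants, measurements or software. The downsides are that about 15 per arm requires the small-sample degrees-of-freedom correction, that bias is removed only when drop-out depends on observed data, and that no post-baseline information is recovered from people who leave on Day 1.

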5 SAFETY

5.1 Definition and Assessment of (Serious) Adverse Events and other safety related events

Adverse Event (AE) (Art. 2 para. 57 MDR)

Any adverse medical event, unintentional illness or injury, or adverse clinical sign (including abnormal laboratory findings) in subjects, users, or others, whether or not related to the medical device (MP).

These include events related to the MP or comparator product being studied, as well as the associated procedures. For users or other persons, this is limited to events that are related to the MP.

Serious Adverse Event (SAE) (Art. 2 para. 58 MDR)

An adverse event that resulted in one of the following:

- (a) death;
- (b) serious deterioration in the subject's health resulting in any of the following:
 - (i) life-threatening illness or injury,
 - (ii) permanent impairment of a body structure or function,
 - (iii) hospitalization or extension of an existing hospitalization,
 - (iv) medical or surgical intervention to prevent a life-threatening illness or injury or permanent impairment of a body structure or function;
 - (v) chronic illness,
- (c) fetal distress, fetal death, or a congenital physical or mental impairment or birth defect.

Note: Planned hospitalizations due to a pre-existing condition or a procedure specified in the protocol (CIP) without a serious deterioration in the subject's health are not considered SAE.

Device Deficiency (Art. 2 para. 59 MDR)

Shortcomings of a medical device related to the identity, quality, durability, reliability, safety, or performance of an investigational device, including malfunctions, user error, and insufficient information from the manufacturer.

The definition includes defects in both the test product and the comparator product.

Malfunction (ISO14155)

The failure of an investigational product to perform its intended function in accordance with the instructions for use or protocol (CIP).

Defects of the medical device with SAE potential (Device Deficiency with Serious Adverse Event Potential)

(Art. 80 para. 1 letter c MDR; ISO14155)

Any product defect that could have resulted in a serious adverse event if appropriate measures had not been taken, no intervention had been made, or if the circumstances had been less favourable.

Adverse Device Effect (ADE) (ISO14155)

An adverse event that maybe, probably, or causally related to the use of an investigational product or associated procedures.

This includes events resulting from inadequate or incorrect instructions for use, from use, implantation, installation or operation, or from malfunctions of the test product. This also includes events caused by operating errors or intentional misuse.

Serious Adverse Device Effect (SADE) (ISO14155)

An adverse reaction of the medical device (ADE) that has led to one of the consequences of a serious adverse event.

Unanticipated Serious Adverse Device Effect (USADE) (ISO14155)

A serious adverse reaction of the medical device (SADE) that has not been identified in its nature, frequency, severity or outcome in the current version of the risk report.

Note: An anticipated serious adverse reaction of the medical device (Anticipated SADE, ASADE) is an effect that has already been identified in the risk report in terms of type, frequency, severity or outcome.

Causal relationship of SAEs (MDCG 2020-10/1)

The causal relationship with the medical device or the methods of investigation is assessed by the principal investigator and the sponsor as follows:

- Unrelated: The association with the product or process can be excluded.
- Possible: The connection with the use of the test product is weak, but cannot be completely ruled out. Alternative causes are also possible. Cases where assessment is not possible or no information is available are also considered possible.
- Probable: The association with the use of the investigational product appears relevant and/or the event cannot be meaningfully explained by another cause.
- Causal relationship: The serious event is unequivocally related to the investigational product or procedures.

5.2 Documentation and reporting in Medical Device Category A clinical investigations

Device defects (DD) and all adverse events (AE), including all serious adverse events (SAE), are recorded, fully investigated, and documented in the source document as well as in the corresponding Case Report Forms (CRF) throughout the study period, i.e. from the time of patient consent to the last CIP-specific procedure, including a safety follow-up phase.

- **Documentation of AEs (including SAEs)** by the investigator includes diagnosis or symptoms, start and end dates of the event, treatment of the event, resolution of the event, assessment of the severity and causal relationship with the medical device and/or the examination procedure (Art. 32 ClinO-MD, ISO14155).
- **Documentation of DDs** by the auditor includes the description of the event, the start date, information about the examination device, actions taken with respect to the examination device and the determination of whether the DD has resulted in an AE. The sponsor examines all DDs and decides and documents in writing whether they could have led to an SAE (DD with SADE potential) (Art. 32 ClinO-MD, ISO14155).

Reporting of SAEs (Art. 32 ClinO-MD)

All SUEs are documented and reported immediately (within a maximum of 24 hours) to the sponsor/investigator of the investigation.

If it cannot be ruled out that the SUE that occurred in Switzerland is due to the intervention under investigation, the investigator reports it to the Ethics Committee via BASEC within 15 days.

Follow up of (Serious) Adverse Events

An aftercare plan is created for the affected subjects, ensuring that they receive appropriate medical care and support. Communication with the affected subjects is maintained to monitor their recovery.

Notification of safety and protective measures (Art. 32 ClinO-MD)

If immediate safety and protective measures must be taken during the conduct of the investigation, the investigator shall inform the Ethics Committee within 7 days of these measures and the circumstances that require them.

5.2.1 Foreseeable adverse events and anticipated adverse device effects

Predictable AEs during the application of the MD.

Type of event	Description	Mitigation or Treatment Measures	Probable incidence
Skin irritation or redness	Localized erythema or irritation at the application site due to pressure or cold.	use protective materials; apply soothing creams or gels if necessary.	Medium
Pain or discomfort	Temporary pain or discomfort during or after application due to refrigeration.	Ask participants to report pain.	Small
Decreased local sensitivity	Temporary numbness or decreased sensitivity due to exposure to cold.	inform participants about this possibility; Avoid prolonged use to prevent complications.	Medium
Slight swelling or edema	Localized swelling due to prolonged cooling or improper use.	Monitor application time; elevate the affected area; Reduce application time for subsequent applications.	Small

No SAEs are expected.

5.2.2 Reporting of Safety related events

Reporting to the Sponsor:

All Serious Adverse Events (SAEs), Equipment Defects (DDs) with potential for SAEs, and health hazards requiring action will be reported by the investigator (or authorized representative) to the

sponsor immediately upon becoming aware of the event. DDs are evaluated as to whether they could lead to an SAE.

Pregnancies

Pregnant or breastfeeding women are excluded from participating in the examination. Participants who become pregnant during the study must notify the study leader immediately and are not allowed to continue participating in the study. However, the examination does not pose a risk to pregnant women.

Reporting to the Competent Ethics Committee:

The sponsor shall immediately notify the Ethics Committee of any SAE in which a causal relationship between the event and the clinical trial test procedure has been established (Art. 33 ClinO-MD).

To ensure prompt notification, the sponsor may first submit an incomplete notification.

In the event that safety or health risks arise during the conduct of the investigation that require immediate action, the sponsor shall inform the Ethics Committee within 2 days of these measures and the circumstances that made them necessary (Art. 34 ClinO-MD).

Periodic safety reporting (Art. 35 ClinO-MD):

Once a year, the sponsor submits a list of SAEs and DDs to the Ethics Committee and submits a report on their severity, the causal relationship with the device and the intervention, and the safety of the participants. The sponsor informs the Ethics Committee annually about the general progress of the clinical trial.

Materiovigilance reporting to Swissmedic:

The sponsor is responsible for ensuring that Swissmedic is informed of serious incidents in accordance with Art. 66 MedDO.

Mate vigilance reports are not sent to the Ethics Committee.

If the sponsor is not the manufacturer of the device under investigation or the Swiss representative of the manufacturer:

- In the event of incidents, verify that the event has occurred in accordance with Art. 66 para. 4 MedDO is subject to the reporting obligation (using the instructions MU680_20_008e_WL).
- The sponsor must ensure that reportable incidents are sent to Swissmedic using Form MU680_20_015d_FO ([contact]).
- Users are required by law to inform the suppliers of the equipment (Art. 66 para. 4 MedDO).

5.3 Radiation

No radiation is included in this examination.

5.4 Amendments (Art. 15 ClinO-MD)

Significant changes to the study structure, organisation, protocol and associated study documents will be submitted to the Ethics Committee for approval in accordance with Art. 15 ClinO-MD before implementation. In addition, a list of non-material changes is reported annually to the EC, together with the CSA or the *general study progress report*.

5.5 Notification and reporting upon completion, discontinuation or interruption of the

Investigation

After the regular conclusion of the investigation, the Ethics Committee will be informed about BASEC within 30 days in accordance with Article 38 of the ClinO-MD.

The sponsor/investigator may terminate the investigation early in certain circumstances, such as:

- ethical concerns,
- Insufficient participant recruitment,
- doubts about the safety of the participants or if the participants are at risk (e.g. if the benefit-risk assessment is no longer positive),
- Changes in accepted clinical practice that make it no longer make sense to continue the investigation,
- Early indications of harm or benefit of experimental intervention.

In the event of an early termination or interruption of studies, the Ethics Committee will be informed of BASEC within 15 days in accordance with Article 38 of the ClinO-MD.

Within 12 months of completion or termination of the investigation, a final report is submitted to the Ethics Committee via BAREC, unless a longer period is provided for in the protocol (Article 38 ClinO-MD).

